**Table 5.2 Dose Modifications and Dosing Delays for patients demonstrating clinical response or stable disease**

Dose level	Dose of selinexor
Dose level 0	60 mg twice weekly (D1, D3 on weeks 1, 2, 3 of each 4 week cycle)
Dose level -1	40 mg twice weekly (D1, D3 on weeks 1, 2, 3 of each 4 week cycle)
Dose level -2	20 mg twice weekly (D1, D3 on weeks 1, 2, 3 of each 4 week cycle)
Dose level -3	20 mg once weekly (D1 on weeks 1, 2, 3 of each 4 week cycle)
Dose level -4	Discontinue dosing

Patients will continue to receive selinexor until they need to have their dose reduced below 20 mg once weekly dose, at which time treatment will be discontinued.

Treatment or visit delays for public holidays or weather conditions do not constitute a protocol violation.

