Grade 3 (> 3.0 - 10.0 x ULN) Grade 4 (> 10.0 x ULN)	Discontinue selinexor until resolved to Grade ≤2, then follow guidelines above. Note: If Grade 3 or Grade 4 hyperbilirubinemia is due to the indirect component only, and hemolysis as the etiology has been ruled out as per institutional guidelines (e.g. review of peripheral blood smear and haptoglobin determination), then reduce selinexor dose by 1 level (Table 5.2) and continue treatment at the discretion of the investigator. Discontinuation of selinexor is required if concurrent elevations of total bilirubin > 2.0 X upper limit of normal (ULN) and ALT or AST > 3.0 X ULN are observed and other causes have been ruled out. In order to characterize hepatic toxicity more precisely, fractionation of bilirubin and alkaline phosphatases will be required for elevated values > 2.0 X ULN and ≥ CTCAE Grade 2, respectively.
AST or ALT (rare)	
Grade 1 (> ULN - 2.5 x ULN)	Maintain dose level
Grade 2 (> 2.5 - 5.0 x ULN)	Delay selinexor until resolved to Grade ≤1, then maintain dose level. Consider addition of S-adenosylmethionine (SAM) 400mg qd-bid.
Grade 3 (> 5.0 - 20.0 x ULN)	Delay selinexor until resolved to ≤ grade 2, then reduce by 1 dose level (Table 5.2 ). Consider addition of S-adenosylmethionine (SAM) 400mg qd-qid. If no further AST or ALT elevations occur during one cycle (4 weeks) at the reduced dose level, then dose may be continued at the reduced dose. Discontinuation of selinexor is required if concurrent elevations of direct bilirubin > 2.0 X upper limit of normal (ULN) and ALT or AST > 3.0 X ULN are observed. In order to characterize hepatic toxicity more precisely, fractionation of bilirubin and alkaline phosphatases will be required for elevated values > 2.0 X ULN and ≥CTCAE grade 2, respectively.
Grade 4 (> 20.0 x ULN)	Delay selinexor until resolved to ≤ Grade 2, then reduce by 2 dose levels
Cardiac (rare)	
Hypertension	Treatment-emergent hypertension should be treated as per standard cardiology practice. Recommended agents for the management of blood pressure elevations on selinexor include angiotensin-converting enzyme inhibitors and calcium channel blockers.
Grade 1	Maintain dose level

Toxicity and Intensity	Dose Modification

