Grade 2 / 3	Delay selinexor and initiate/intensify antihypertensive therapy. Selinexor may be restarted in conjunction with standard anti-hypertensive medication if BP is controlled (i.e BP $\leq$ 150/100 mmHg). If BP is controlled $\leq$ 7 days after suspending selinexor, maintain dose level If BP is controlled $>$ 7 days after suspending selinexor, then reduce by 1 dose level
Grade 4	Delay the selinexor and initiate/intensify antihypertensive therapy, then reduce by 1 dose level. Selinexor may be restarted in conjunction with anti-hypertensive medication if BP is controlled (i.e BP $\leq$ 150/100 mmHg).
Cardiac – Other (rare)	
Grade 1 or 2	Maintain dose level
Grade 3	Delay selinexor until resolved to $\leq$ Grade 1, then reduce by 1 dose level (Table 5.2).
Grade 4	Discontinue study treatment
Diarrhea (uncommon)	
Grade 1 (despite maximal anti-diarrheal medication)	At the first sign of abdominal cramping, loose stools, or onset of diarrhea, it is recommended that the patient be treated according to institutional standard of care. Maintain dose level of selinexor.
Grade 2 (despite maximal anti-diarrheal medication)	Reduce to selinexor to one weekly until resolved to $\leq$ grade 1, then re-start twice weekly at the current dose level. If diarrhea returns as $\geq$ Grade 2, then reduce selinexor dose by one dose level and dose once weekly until resolved to $\leq$ grade 1, then re-start twice weekly at reduced dose level
Grade 3/4 (despite maximal anti-diarrheal medication)	Delay selinexor until resolved to $\leq$ grade 2, then re-start twice weekly at reduced dose level
Neurotoxicity (not observed to date)	
CTCAE grade 1 / 2	Grade 0 $\rightarrow$ Grade 1: maintain dose level Grade 0 or 1 $\rightarrow$ Grade 2 : delay study treatment until resolved to $\leq$ Grade 1, then reduce by 1 dose level (Table 5.2).
CTCAE grade 3	Discontinue study treatment until resolved to Grade $\leq$ 1 then reduce by 2 dose levels (Table 5.2 ).
CTCAE grade 4	Discontinue study treatment.
Amylase and/or lipase elevations (rare)	
Grade 1 or 2	Maintain dose level

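### Table 5.3 states the mandatory combined liver stop twice with different triggers, and no text says it prevails over the single-analyte rows that let dosing resume or continue

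*Combined protocol and SAP*

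**What the plan says.** All of this is in Table 5.3 of the protocol unless stated otherwise.

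- **Stop, total version** (bilirubin Grade 3/4 row, > 3.0 × ULN): "Discontinuation of selinexor is required if concurrent elevations of total bilirubin > 2.0 X upper limit of normal (ULN) and ALT or AST" exceeds 3.0 × ULN, subject to the condition "ULN are observed and other causes have been ruled out".
- **Stop, direct version** (AST/ALT Grade 3 row, > 5.0–20.0 × ULN): "Discontinuation of selinexor is required if concurrent elevations of direct bilirubin > 2.0 X upper limit of normal (ULN) and ALT or AST" exceeds 3.0 × ULN. There is no condition about other causes.
- **AST/ALT Grade 2** (> 2.5–5.0 × ULN): "Delay selinexor until resolved to Grade ≤1, then maintain dose level".
- **AST/ALT Grade 4** (> 20.0 × ULN): "Delay selinexor until resolved to ≤ Grade 2, then reduce by 2 dose levels". From the starting level this is dose level -2 in Table 5.2, "20 mg twice weekly (D1, D3 on weeks 1, 2, 3 of each 4 week cycle").
- **Total bilirubin 1.5–3 × ULN**: dose once weekly until Grade 1 or lower, then return to twice weekly.
- **Indirect-only note** (bilirubin Grade 3/4 row): if only the indirect component is raised and hemolysis is excluded, "then reduce selinexor dose by 1 level (Table 5.2) and continue treatment at the discretion of the investigator".

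The last four instructions do not mention the combined stop or exempt patients who meet it. Section 5.3 and the notes to Table 5.3 say that the worst toxicity governs dose changes. The notes also end treatment after a drug-related interruption of more than 21 days; section 5.2 allows an exception for clinical benefit.

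**The concern.** A combined rise in bilirubin and transaminases is a signal on which the protocol makes stopping mandatory. Its trigger should therefore be the same wherever it is stated, and its rank over the other rows should be clear. Here the two statements differ in the bilirubin fraction and in whether other causes must first be excluded. A site that looks up the patient's own grade may find no stop at all, only an instruction to hold and restart or to go on at a lower frequency. Section 3.1 plans a multicenter study, so the same liver signal could end treatment at one site and lead to resumed or continued dosing at another.

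**Working it through.** No figure in the plan has to be reproduced. The check sets the rows side by side. Values are multiples of ULN. The patients below are illustrative, not trial data.

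**1. Triggers against the rows that hold them.** The total version triggers at bilirubin > 2.0, but its row starts at > 3.0, so > 2–3 lies outside. The direct version triggers at ALT/AST > 3.0, but its row covers > 5.0–20.0, so > 3–5 and > 20 lie outside.

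**2. Row-bound reading (a sentence applies only in its own row).** Crossing 2 bilirubin bands with 3 ALT/AST bands gives 2 × 3 = 6 combinations. The stop text found in the applicable rows is:

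| Total bilirubin | ALT/AST > 3–5 | ALT/AST > 5–20 | ALT/AST > 20 |
|---|---|---|---|
| > 2–3 | none | direct | none |
| > 3 | total | total and direct | total |

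Four of 6 have some stop text and 2 of 6 have none. One of the empty cells is in the most severe transaminase band. The grid is indexed by total bilirubin. The documents give no reference limits for either fraction, so a patient with direct > 2 and total not > 2 cannot be ruled out and is not counted.

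**3. General reading (the sentences apply in every row).** All six combinations are then covered, and the question becomes which instruction prevails:

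| Patient | Total | Direct | ALT | Other causes | Total version | Direct version | Bilirubin row | AST/ALT row |
|---|---|---|---|---|---|---|---|---|
| A | 2.5 | 1.5 | 4 | ruled out | met | not met | once weekly, then twice weekly | hold, same dose |
| B | 2.5 | 2.2 | 4 | not yet ruled out | not met | met | once weekly, then twice weekly | hold, same dose |
| C | 2.5 | 2.2 | 25 | ruled out | met | met | once weekly, then twice weekly | hold, two levels lower |
| D | 4 | 1.0 | 3.5 | ruled out, including hemolysis | met | not met | indirect-only note: one level lower, continue | hold, same dose |

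A and B show that the versions differ in both directions. In all four patients a stop is mandatory under one version or both, while the single-analyte rows allow dosing to continue or resume. ALT/AST of 2.5–3.0 never triggers, so the Grade 2 conflict is confined to > 3–5.

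**4. Does any text settle the order?** The worst-toxicity texts rank toxicities, not a stop against a restart. For A and B they do not even rank the two analytes: the bilirubin 1.5–3 row lies just below Grade 3 and asks for recovery to Grade 1, so it reads as Grade 2, the same grade as ALT 4. Section 5.2 appeals to clinical judgment. Section 7.7 permits re-challenge for selected events that it does not name. None gives the combined stop precedence.

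**5. Doses under the single-analyte rows.** These start from 60 mg with six doses per cycle (section 1.4, Table 5.2):
- AST/ALT Grade 2, once bilirubin has also recovered: 60 × 6 = 360 mg per cycle.
- AST/ALT Grade 4, once bilirubin has also recovered: 20 × 6 = 120 mg per cycle.
- Bilirubin 1.5–3 row, assuming 60 mg once in each of weeks 1–3: 60 × 3 = 180 mg per cycle.
- Indirect-only note: 40 × 6 = 240 mg per cycle.

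Under the combined stop no drug is given for as long as the discontinuation lasts.

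**The case against.** The best defence is that each stop sentence gives a sufficient condition. Neither says that it is the only one, so meeting either requires discontinuation. Thresholds of 2 and 3 × ULN would also have little purpose in rows that start at 3 and 5 × ULN unless they were meant to reach further. On that reading the stop is a specific exception to the general grade rows. This stands as an argument about intent. A reader might infer that the two sentences contradict each other and leave A or B without an instruction; the text does not support that. It does not, however, say that the stop overrides rows that cover a whole grade without exception.

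Three other stronger readings go too far:

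- **Drug is held in every triggering case.** Every AST/ALT row above 3 × ULN does order a hold. The bilirubin 1.5–3 row and the indirect-only note keep patients on drug, and nothing says that the AST/ALT row outranks them. Nor can one conclude that such patients would stay on drug; a cautious site would hold.
- **The choice is between a permanent stop and full dose.** Permanence is the natural reading, because neither stop sentence has an until-clause. The table says "Discontinue study treatment" without one for Grade 4 neurotoxicity, Grade 4 other cardiac events and pancreatitis of Grade 2 or above. But it also uses the verb for temporary holds, and the row for other Grade 4 events allows a restart if another cause is found. The doses above are therefore illustrative.
- **Many patients are affected.** Table 5.3 labels hepatic events rare and no rate is given. After a hold, the 21-day limit leaves the conflict mainly to those who recover sooner or fall under the clinical-benefit exception.

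**Conclusion.** The inconsistency is real and minor. One mandatory safety rule has two triggers, each placed in a row that starts above its own threshold. Three other rows and the indirect-only note give triggering patients a different instruction, and no text sets the order. The 2-of-6 count depends on the row-bound reading. On the general reading the coverage gap closes and the missing precedence remains; the two arguments should not be added together. The size in patients cannot be given. The primary analysis, sample size and error rates are not touched.

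**What to change.** Move the rule to one stand-alone hepatic row in Table 5.3 that expressly overrides every single-analyte bilirubin and AST/ALT row, including bilirubin 1.5–3 × ULN, AST/ALT Grade 4 and the indirect-only note. The row should say:

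1. Withhold selinexor at once when ALT or AST > 3 × ULN occurs with total or direct bilirubin > 2 × ULN.
2. Discontinue if direct bilirubin is > 2 × ULN (unconditional, as now), or if total bilirubin is > 2 × ULN and other causes are ruled out.
3. Do not restart under the single-analyte rows. The discontinuation is permanent, and re-challenge under section 7.7 does not apply.

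The row should also say what happens to a patient held on total bilirubin alone in whom another cause is found. The documents do not settle that clinical choice.

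One shared clause on other causes would look tidier, but it would relax a direct-bilirubin stop that is now unconditional. That is a clinical trade-off, not a clarification.

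The downside is that a few patients, some with indirect-only elevation, may stop drug who would otherwise have resumed. No new tests are needed: total bilirubin, ALT and AST are in the chemistry panel, and Table 5.3 already requires fractionation above 2.0 × ULN (that sentence should move to the new row). The cost is an amendment with PRC and IRB approval and notice to sites, as section 9.4 requires.

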This Phase 2 study will begin dosing selinexor at 60 mg flat dose, twice per week at least 48 hours apart (Mon/Wed, Tue/Thurs or Wed/Fri) on Weeks 1, 2 and 3 of a 4-week cycle. Recent analysis of the existing PK data from Phase 1 trials KCP-330-001 and KCP-330-002 supports the use of fixed rather than BSA-based dosing. The 5th and 95th percentile for BSA values encountered to date in Phase 1 trials KCP-330-001 and KCP-330-002 are 1.5 and 2.3 m^2, respectively (N=331). PK values ( $C_{max}$  and  $AUC^{(0-\infty)}$ ) for a given flat (fixed) dose of selinexor were similar across this typical BSA range, indicating that exposure is not strongly correlated with BSA. Selinexor will not be taken during Week 4 (total six doses per cycle). Cycles are repeated every 28 days until disease progression. For each patient, dose reductions of Selinexor is allowed until the dose has been reduced below 20 mg dose per week, at which time treatment will be discontinued.

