**Table 5.2.1 Regimen Description**

Study Drug	Premedication; precautions	Dose	Route	Schedule	Cycle Length
Selinexor	Pre-medicate with ondansetron 8 mg PO q8h on D0-D3 and olanzapine (2.5-5.0 mg QHS) on D1 and D3*	60 mg	Oral	Ondansetron: four-times weekly (D0 – D3) of each 4-week cycle. Olanzapine: Twice weekly (D1 and D3 of each week 1 – 3 of each 4-week cycle. Drug holiday on week 4).	4 weeks (28 days)

\*Prophylaxis prior to initiation of therapy with selinexor is recommended.

Selinexor will be administered at a starting dose of 60 mg on D1 and D3 of weeks 1 – 3 of each 4 week cycle, with subsequent dose titration for dose limiting toxicity (Table 5.3).

- All adjustments of dose must be maintained either in the pharmacy records or subject’s medical records.

Number of Tablets per Total Mg Dose		
Mg Dose (from Rounded Dose Table)	Number of Tablets of Each Strength	
	10 mg tablets	25 mg tablets
20	2	0
40	4	0
60	1	2

Patients will receive prophylactic treatment to prevent anorexia and nausea, which will include the following:

- Ondansetron 8 mg PO q8h on day prior to and day of dosing (D0-D3)
- Olanzapine 5 mg PO qbedtime or 2.5 mg PO BID on day of dosing (D1, D3)

If nausea and/or anorexia persist despite administration of ondansetron and olanzapine on the days of dosing, additional prophylactic treatment may include the addition of any of the following:

- Dexamethasone 2-4 mg PO BID on days of dosing (D1, D3)  
AND/OR
- Olanzapine 5 mg PO qbedtime or 2.5 mg PO BID on days prior to dosing (D0, D2)  
AND/OR
- Megestrol acetate 160-400 mg daily, 0-3 days before the first dosing day of KPT-330  
AND/OR
- Mirtazapine 15 mg qd (qpm/qhs), 0-3 days before the first dosing day of KPT-330  
AND/OR
- Marinol 5 mg PO BID  
AND/OR
- NK1R antagonist: Aprepitant 120 mg PO x1 on D1, then 80 PO qAM on D2-D3 of each dosing week or equivalent should be considered and will be covered for selected patients who have severe nausea and vomiting.

If the patient is on steroids coming on the study, megestrol acetate should be added prophylactically to prevent anorexia. Other androgenic-anabolic steroids including exogenous testosterone or synthetic testosterone derivatives (e.g., oxandrolone) are contraindicated in patients with metastatic castration resistant prostate cancer, and therefore must not be administered at any point during trial participation.

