**Table 5.3 Criteria for dose adjustments of Selinexor-related toxicities**

Toxicity and Intensity	Dose Modification
Fatigue (common)	
Grade 1	Insure adequate caloric intake and assess volume status. Adjust other medications. Consider addition/increased dose of corticosteroids (e.g., 2-4 mg BID dexamethasone the day of selinexor dosing). Rule out other causes of fatigue such as adrenal insufficiency or thyroid dysfunction.
Grade 2	Insure adequate caloric and fluid intake and assess volume status. May consider additional corticosteroid, per clinician discretion. If fatigue dose not resolve to Grade 1, reduce dose of selinexor by one level (Table 5.2).
Grade 3	Insure adequate caloric and fluid intake and assess volume status. Interrupt selinexor dosing until resolved to Grade $\leq$ 2, reduce dose of selinexor by 1 level (Table 5.2).
Anorexia (common)	
Grade 1	Assess dietary options (e.g. try a variety of other foods). Add high-calorie supplements (e.g., Ensure®). If fatigue or nausea also present, consider addition/increased dose of dexamethasone (e.g., 2-4 mg dexamethasone BID on the day of selinexor dosing), or consider addition of other anti-emetic per section 5.1

Toxicity and Intensity	Dose Modification
Grade 2	Add high-calorie supplements (e.g., Ensure®). Consider addition/increased dose of dexamethasone (e.g., 2-4mg dexamethasone BID on the day of selinexor dosing and/or on the day prior to dosing, or consider addition of other anti-emetic per section 5.1. Consider dronabinol (Marinol®). Skip intermittent doses of selinexor while supportive medications are instituted. If Grade 2 anorexia does not resolve after institution of supportive medications, reduce selinexor dose by 1 level (Table 5.2).
Grade 3	Interrupt dosing with selinexor. Add high calorie supplements. Use supportive medications alone or in combinations. Restart selinexor at 1 dose level reduction (Table 3) once anorexia resolves to Grade ≤2. If Grade 2 anorexia persists with supportive medications, reduce dose of selinexor another level (Table 5.2).
Nausea/Emesis (common)	
Grade 1	D2 antagonists, addition/increased dose of corticosteroids (e.g., 2-4mg dexamethasone with each dose of selinexor the day prior to dosing), NK1 antagonists, or dronabinol (Marinol) or combinations can prevent nausea in the majority of patients.

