
Notes: All dose modifications should be based on the worst preceding toxicity.
 
Isolated values of <math>\geq</math> grade 3 alkaline phosphatase values will NOT require dose interruption. Determination of liver vs. bone etiology should be made, and evaluation of GGT, 5'NT, or other liver enzymes should be performed.
 
<math>\geq</math> Grade 3 anemia judged to be a hemolytic process secondary to study drug will require interruption of study treatment until resolved to <math>\leq</math> Grade 1. Selinexor may then be re-instituted at 2 levels below original dose (Table 5.2 ).
 
<math>\geq</math> Grade 3 lymphopenia considered clinically significant will require dose interruption until resolved to <math>\leq</math> grade 2, then reduce by 1 dose level.
 
Patients are allowed dose reductions to a minimum dose of 35 mg/m^2 as described in Table 5.2
 
If a patient requires a dose interruption of >21 days due to a study drug related toxicity, then the patient must be discontinued from the study. Patients who discontinue the study for a study related adverse event or abnormal laboratory value must be followed at least once a week for 28 days and subsequently at 28 day intervals until resolution or stabilization of the event, whichever comes first.
	

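### The Table 5.3 Notes set a 35 mg/m² minimum dose that rules out every reduced level in Table 5.2, and their 21-day stopping rule omits the exception in section 5.2

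*Combined protocol and SAP*

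**What the plan says.** The dosing limits appear in four places.

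- **Table 5.3, Notes.** "Patients are allowed dose reductions to a minimum dose of 35 mg/m" (the unit is mg/m²), with Table 5.2 given as the source.
- **Table 5.2 and the text below it.** Level 0 is 60 mg twice weekly, level -1 is 40 mg twice weekly, level -2 is 20 mg twice weekly, level -3 is 20 mg once weekly, and level -4 is discontinuation. The stated floor is: "Patients will continue to receive selinexor until they need to have their dose reduced below 20 mg once weekly dose".
- **Section 1.4.** The same floor is given: "dose reductions of Selinexor is allowed until the dose has been reduced below 20 mg dose per week". This section also says that the phase 1 pharmacokinetic analysis "supports the use of fixed rather than BSA-based dosing".
- **Section 5.1, tablet table.** Only 20, 40 and 60 mg are listed.

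The Notes also deal with haemolytic anaemia: "Selinexor may then be re-instituted at 2 levels below original dose". From a 60 mg start, two levels down is 20 mg twice weekly.

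On long treatment gaps, section 5.2 requires discontinuation after a delay of more than 21 days for drug-related toxicity, unless the patient is benefiting clinically. Such a patient may continue if the investigator judges it to be in his best interest and the drug supplier approves. The Table 5.3 Notes give the same 21-day limit with no exception.

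**The concern.** The note cites a table that contradicts it in both unit and value. Taken at its word, it forbids every reduced dose that Table 5.3 tells sites to use and leaves only full dose or stopping. Table 5.3 is what a site consults when a patient has toxicity, and this is a multicentre trial, so sites could read the limit differently. The possible results are inconsistent dosing, avoidable discontinuations and avoidable protocol deviations.

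The 21-day mismatch concerns an identifiable patient: one who is benefiting but needs more than 21 days to recover from toxicity. Section 5.2 allows him to stay on drug; the Notes require him to stop.

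**Working it through.** **Inputs.** The note's floor is 35 mg/m² (Table 5.3 Notes). The flat doses are 60, 40 and 20 mg (Table 5.2). The BSA range is the 5th to 95th percentile in section 1.4: "encountered to date in Phase 1 trials KCP-330-001 and KCP-330-002 are 1.5 and 2.3 m" (m², N=331).

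**Can the note's figure be found in the table it cites?** No. Table 5.2 contains no dose per m², so 35 mg/m² cannot be reproduced from it.

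**Conversion.** Floor in mg = 35 × BSA. Flat dose in mg/m² = dose ÷ BSA. Share of the floor = dose ÷ (35 × BSA).

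| | BSA 1.5 m² | BSA 2.3 m² |
|---|---|---|
| Floor of 35 mg/m², in mg | 35 × 1.5 = 52.5 | 35 × 2.3 = 80.5 |
| 60 mg (level 0), mg/m² | 40.0 | 26.1 |
| 40 mg (level -1), mg/m² | 26.7 (76% of floor) | 17.4 (50%) |
| 20 mg (levels -2 and -3), mg/m² | 13.3 (38%) | 8.7 (25%) |

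**Largest BSA at which each dose meets the floor (dose ÷ 35).** 40 mg: 40/35 = 1.14 m². 20 mg: 20/35 = 0.57 m². Both lie below the 5th percentile of 1.5 m², so all three reduced levels fail across the range. For 60 mg the limit is 60/35 = 1.71 m², so even the starting dose is below the note's floor for patients with a larger BSA.

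**Alternative reading as a weekly total.** Level -1 gives 80 mg per week, or 53.3 mg/m² at 1.5 m² and 34.8 mg/m² at 2.3 m². It meets 35 up to 80/35 = 2.29 m². Level -2 (40 mg per week) gives 26.7 to 17.4 mg/m², and level -3 (20 mg per week) gives 13.3 to 8.7 mg/m². Both still fail throughout, so this reading does not rescue the note.

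**Conflict within Table 5.3.** Besides haemolytic anaemia in the Notes, three rows call for a two-level reduction: AST or ALT Grade 4, neurotoxicity grade 3, and symptomatic Grade 3 or 4 amylase or lipase elevation. From 60 mg each leads to 20 mg twice weekly, which the note would bar.

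**The 21-day rules side by side.**

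| Patient with a gap of more than 21 days from drug-related toxicity | Section 5.2 | Table 5.3 Notes |
|---|---|---|
| No clinical benefit | Discontinue | Discontinue |
| Clinical benefit, investigator in favour, supplier approves | May continue | Discontinue |

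Section 5.2 speaks of a delay and the Notes of an interruption. The protocol does not define these terms separately, and Table 5.3 uses both for withholding drug until recovery, so the choice of word does not separate the two rules.

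**Leftover references.** The anorexia Grade 3 row says "Restart selinexor at 1 dose level reduction (Table 3) once anorexia resolves", and the asymptomatic amylase or lipase row also cites a Table 3. The tablet table heading reads "Mg Dose (from Rounded Dose Table". Neither table appears in the protocol.

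**Statistical design.** The two-stage figures in section 8.2.1 do not depend on any of this. By exact binomial calculation, early stopping under the null is 0.6085, type I error 0.0477 and power 0.9007, against the stated 60.9%, 0.048 and 90.0%.

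**The case against.** The best defence is that the note is harmless. It sends the reader to Table 5.2, where the flat levels and the 20 mg once-weekly floor are plain. Section 5.3 and most rows of Table 5.3 also point to Table 5.2. A floor that exceeds the starting dose above 1.71 m² is visibly a leftover, and applying it would need a BSA value that the assessment schedule does not list. On the 21-day rule, section 5.2 is the fuller text, and its exception cannot be used without contacting the drug supplier, which would bring the question into the open.

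Much of this stands for the floor: a careful reader can recover the intended value, and no mis-dosed patient has been shown. It does not make the note correct. The note is a dosing limit in the current text, and it contradicts the instructions beside it. For the 21-day rule the defence is weaker. Both statements are mandatory, nothing says which prevails, and a site that follows the Notes would stop the patient without ever contacting the supplier. The stale table references are minor, since neighbouring rows make the target clear.

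**Conclusion.** The concern holds. The 35 mg/m² floor is a wording error: at 52.5 to 80.5 mg per dose it lies above all three reduced levels for any BSA from 1.5 to 2.3 m². That result assumes trial patients fall within the phase 1 BSA range in section 1.4, but the margin is wide, because 40 mg would pass only at 1.14 m² or less. The figure looks like a remnant of BSA-based dosing, though that is an inference. The 21-day conflict is a real difference in instruction, and the documents do not settle it.

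Both should be corrected because they govern dosing and discontinuation. No effect on sample size, type I error, power or week-16 progression status is claimed.

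**What to change.** 1. In the Table 5.3 Notes, replace the 35 mg/m² sentence with one saying that selinexor may be reduced to, but not below, 20 mg once weekly (dose level -3, Table 5.2).
2. Make the 21-day rules agree. Either add to the Notes that the clinical-benefit and approval exception in section 5.2 applies, or delete that exception from section 5.2. The sponsor must decide which rule stands.
3. Optional tidying in the same amendment: change Table 3 to Table 5.2 in the anorexia Grade 3 and asymptomatic amylase or lipase rows, remove the Rounded Dose Table reference from the tablet table heading, and have the interim toxicity rule in section 8.3 cite Table 5.2 where it refers to dose levels. That rule already points naturally to Table 5.2.

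The cost is a wording amendment, with no added procedures and no change to the statistical design.
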